Data Monitoring Plan: Subjective and behavioral data will be collected using standardized computerized measures. Brain imaging data will be identified with the study ID only and sent to a server owned by the PI by the MRISC staff. Hormonal data obtained from blood sample assays will also be sent to the PI by the analyzing laboratory. All subject data (subjective, behavioral, fMRI, and hormonal) will only be identified with the subject's ID. The PI will keep the codes that link the name of the participant and the study ID confidential in a password protected file on a password protected computer. Data from paper forms will be entered in the computer. Data will be analyzed using the general linear model and regression analyses within SPM and SPSS.

Safety Monitoring Plan: We will recruit healthy volunteers aged 21-29 years. Potential volunteers will be screened for physical and psychiatric health. Women will provide a urine sample for a pregnancy test before each session. Exclusion criteria are any serious medical conditions requiring medication, current or past medical condition considered to be a contraindication for study condition, any current Axis I psychiatric disorder, including substance use disorders, any history of psychosis, less than a high school education, lack of fluency in English, and contraindication for MRI scanning (i.e., claustrophobia, pacemaker, heart valves). Women will be accepted only if they are not pregnant, lactating, or planning to become pregnant.

Subjects will attend an orientation session during which they will sign the consent form and be instructed on the procedures of the study. All subjects will be monitored for recent alcohol and drug use prior to each session. Those with positive tests will be rescheduled or dropped from the study. All fMRI sessions are conducted in a hospital setting. During the sessions, emergency medical assistance will be available by paging the Study Physician, the psychiatrist resident on call, or the general emergency number for the hospital. Alternately, the subject may be transported to the emergency room. All adverse events (AEs) and unanticipated problems occurring during the course of the study will be reported to the IRB by the PI. All AEs will be followed until resolved satisfactorily. If deemed necessary by a physician, a subject may be withdrawn from the study. AEs will be evaluated for serious adverse event (SAE) criteria (defined by the FDA). If an SAE should occur, it will be reported to the IRB, NIAAA, and the FDA. The initial report will be followed by a complete SAE report, sent to all three institutions. If a subject from the study or the investigator discontinues a subject's participation due to an SAE, the patient will receive follow-up medical care as necessary. Follow-up care will continue until the subject no longer requires hospitalization, the condition is stabilized with no future change expected, or the problem is determined to be unrelated to the alcohol administered in the study. The outcome of the SAEs will be reported to NIAAA. The annual progress report submitted to NIAAA will contain a summary of any SAEs occurring in the previous year.

[Back to Top](#)

Future Use and Sharing of Material (e.g., Data/Specimens/Information)

If the material collected for this study will be used by members of the research team or shared with other researchers for future studies, please address the following:

- list the biological specimens and/or information that will be kept
- briefly describe the types, categories and/or purposes of the future research
- describe any risks of the additional use
- describe privacy/confidentiality protections that will be put into place
- describe the period of time specimens/information may be used
- describe procedures for sharing specimens/information with secondary researchers
- describe the process for, and limitations to, withdrawal of specimens/data

N/A

Are you recruiting or expect to enroll **Non-English Speaking Subjects or Subjects from a Foreign Culture?** (does not include short form use for incidentally encountered non-English subjects)

Yes No

Non-English Speaking Subjects or Subjects from a Foreign Culture

Recruitment and Consent:

Describe how information about the study will be communicated to potential subjects appropriate for their culture, and if necessary, how new information about the research may be relayed to subjects during the study.

When recruiting Non-English-speaking subjects, provide a consent document in the subject's primary language. After saving this section, attach both the English and translated consent documents in the "Informed Consent" section.

Cultural and Language Consultants:

The PI is required to identify someone who is willing to serve as the cultural consultant to the IRB.

- This person should be familiar with the culture of the subject population and/or be able to verify that translated documents are the equivalent of the English version of documents submitted.
- The consultant should not be involved with the study or have any interest in its IRB approval.
- Please include the name, address, telephone number, and email of the person who agrees to be the cultural consultant for your study.
- ORI staff will facilitate the review process with your consultant. Please do not ask them to review your protocol separately.

For more details, see the IRB Application Instructions on [Research Involving Non-English Speaking Subjects or Subjects from a Foreign Culture](#).

Local Requirements:

If you will conduct research at an international location, identify and describe:

- relevant local regulations
- data privacy regulations
- applicable laws
- ethics review requirements for human subject protection

Please provide links or sources where possible. If the project has been or will be reviewed by a local ethics review board, attach a copy in the "Additional Information/Materials" section. You may also consult the current edition of the [International Compilation of Human Research Standards](#)

Does your study involve **HIV/AIDS research and/or screening for other reportable diseases (e.g., Hepatitis C)**?

Yes No

HIV/AIDS Research

If you have questions about what constitutes a reportable disease and/or condition in the state of Kentucky, see ORI's summary sheet: "Reporting Requirements for Diseases and Conditions in Kentucky" [\[PDF\]](#).

HIV/AIDS Research: There are additional IRB requirements for designing and implementing the research and for obtaining informed consent. Describe additional safeguards to minimize risk to subjects in the space provided below.

For additional information, visit the online [IRB Survival Handbook](#) to download a copy of the "Medical IRB's requirements for Protection of Human Subjects in Research Involving HIV Testing" [D65.0000] [\[PDF\]](#), and visit the [Office for Human Research Protections web site](#) for statements on AIDS research, or contact the Office of Research Integrity at [contact].

PI-Sponsored FDA-Regulated Research

Is this an investigator-initiated study that:

- 1) involves testing a Nonsignificant Risk (NSR) Device, or
- 2) is being conducted under an investigator-held Investigational New Drug (IND) or Investigational Device Exemption (IDE)?

Yes No

PI-Sponsored FDA-Regulated Research

If the answer above is yes, then the investigator assumes the regulatory responsibilities of both the investigator and sponsor. The Office of Research Integrity provides a summary list of sponsor IND regulatory requirements for drug trials [\[PDF\]](#), IDE regulatory requirements for SR device trials [\[PDF\]](#), and abbreviated regulatory requirements for NSR device trials [\[PDF\]](#). For detailed descriptions see [FDA Responsibilities for Device Study Sponsors](#) or [FDA Responsibilities for IND Drug Study Sponsor-Investigators](#).

- Describe the experience/knowledge/training (if any) of the investigator serving as a sponsor (e.g., previously held an IND/IDE); and
- Indicate if any sponsor obligations have been transferred to a commercial sponsor, contract research organization (CRO), contract monitor, or other entity (provide details or attach FDA 1571).

IRB policy requires mandatory training for all investigators who are also FDA-regulated sponsors (see [Sponsor-Investigator FAQs](#)). A sponsor-investigator must complete the applicable Office of Research Integrity web based training, (drug or device) before final IRB approval is granted.

Has the sponsor-investigator completed the mandatory PI-sponsor training prior to this submission?

Yes No

If the sponsor-investigator has completed equivalent sponsor-investigator training, submit documentation of the content for the IRB's consideration.

[Attachments](#)

HIPAA

0 unresolved
comment(s)

Is HIPAA applicable? Yes No

(Visit ORI's [Health Insurance Portability and Accountability Act \(HIPAA\) web page](#) to determine if your research falls under the HIPAA Privacy Regulation.)

If yes, check below all that apply and attach the applicable document(s): [i](#)

- HIPAA De-identification Certification Form
- HIPAA Waiver of Authorization

Attachments

STUDY DRUG INFORMATION

0 unresolved
comment(s)

The term drug may include:

- FDA approved drugs,
- unapproved use of approved drugs,
- investigational drugs or biologics,
- other compounds or products intended to affect structure or function of the body, and/or
- [complementary and alternative medicine products](#) such as dietary supplements, substances generally recognized as safe (GRAS) when used to diagnose, cure mitigate, treat or prevent disease, or clinical studies of [e-cigarettes](#) examining a potential therapeutic purpose.

Does this protocol involve a drug including an FDA approved drug; unapproved use of an FDA approved drug; and/or an investigational drug?

 Yes NoIf yes, complete the questions below. Additional [study drug guidance](#).

LIST EACH DRUG INVOLVED IN STUDY IN THE SPACE BELOW

Drug Name:

ethanol

Note: Inpatient studies are required by Hospital Policy to utilize [Investigational Drug Service \(IDS\) pharmacies \(Oncology or Non-Oncology\)](#). Use of IDS is highly recommended, but optional for outpatient studies. Outpatient studies not using IDS services are subject to periodic inspection by the IDS for compliance with drug accountability good clinical practices.

Indicate where study drug(s) will be housed and managed:

 Investigational Drug Service (IDS) UK Hospital

Other Location:

Is the study being conducted under a valid Investigational New Drug (IND) application?

 Yes No

If Yes, list IND #(s) and complete the following:

IND Submitted/Held by:

Sponsor: Held By: Investigator: Held By: Other: Held By: Checkmark if the study is being conducted under FDA's Expanded Access Program (e.g., Treatment IND) or if this is an Individual Patient Expanded Access IND ([FDA Form 3926](#)).[FDA's Expanded Access Program Information for Individual Patient Expanded Access INDs](#), and attach the following:

- [FDA Form 3926](#);
- FDA expanded access approval or correspondence;
- Confirmation of agreement from manufacturer or entity authorized to provide access to the product.

For guidance and reporting requirements at the conclusion of treatment see the [Expanded Access SOP](#).

Complete and attach the required [Study Drug Form](#) picking "Study Drug Form" for the document type. Applicable drug documentation (e.g., Investigator Brochure; approved labeling; publication; FDA correspondence, etc.) should be attached using "Other Drug Documentation" for the document type.

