Stop Signal Task: While in the scanner, participants will complete three runs of the stop signal task, adapted and validated for use in fMRI (Kareken et al. 2013). Participants are instructed to respond as quickly as possible when a 'go' target appears (left or right arrow) by hitting the corresponding left or right button on the MRI-compatible keypad. They are also instructed to inhibit that response when a 'stop' signal (a red vertical arrow) occasionally occurs. Each run consists of 80 'go' trials and 40 'stop' trials. The duration of the delay to presentation of the stop signal following the go signal is adjusted until the participant is able to successfully inhibit the response on 50% of trials. The final mean delay of the stop signal, based on this 50% success rate criterion, is subtracted from the mean go reaction time, providing the stop signal reaction time (SSRT), which is the behavioral measure of response inhibition. The BOLD contrast of interest will be activation during correct inhibition trials compared to correct go trials [StopInh>Go].

Hormone assays: Serum assays of estradiol, progesterone, and testosterone will be analyzed by the CCTS Biomarker Analysis Lab.

Subjective Alcohol Effects: Subjective reports of mood and drug effects will be assessed using the BAES (a 14-item scale that measures stimulation and sedation) and the DEQ (a 100 mm visual analogue scale that measures the following: feel substance, like substance, and want more of the substance). Both scales have well-documented validity.

Attachments

Attach Type	File Name
DataCollection	UPPS-P-PaperCopy.doc
DataCollection	AUDIT.docx
DataCollection	BAESPaperCopy.doc
DataCollection	DEQ paper version.doc
DataCollection	TLFB.docx
DataCollection	BIS questionnaire.pdf

Resources

Describe the availability of the resources and adequacy of the facilities that you will use to perform the research. Such resources may include:

- Staffing and personnel, in terms of availability, number, expertise, and experience;
- Computer or other technological resources, mobile or otherwise, required or created during the conduct of the research;
- Psychological, social, or medical services, including equipment needed to protect subjects, medical monitoring, ancillary care, or counseling or social support services that may be required because of research participation;
- Resources for communication with subjects, such as language translation/interpretation services.

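### SSRT is scored as mean go RT minus the tracked delay, so right skew inflates this secondary measure and a longer slow tail under alcohol could pass for poorer stopping

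*Combined protocol and SAP*

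**What the plan says.** All of the scoring text is in Data Collection & Research Materials, under Stop Signal Task. The stop delay "is adjusted until the participant is able to successfully inhibit the response on 50% of trials". To form the score, the average delay reached under that rule "is subtracted from the mean go reaction time, providing the stop signal reaction time (SSRT" in the plan's abbreviation. The plan calls SSRT the score "which is the behavioral measure of response inhibition". On trial numbers, "participants will complete three runs of the stop signal task", and "Each run consists of 80 'go' trials and 40 'stop' trials".

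The plan gives no median or quantile variant, no RT trimming, no rule for omitted go responses, and no check on skew or slowing. It also does not give the staircase step or say which delays form the final mean.

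On the role of SSRT, Study Design makes BOLD activation the primary outcome, and all four aims under Objectives concern that activation. The Statistical Analysis Plan lists regressions and a between-sex t test on the BOLD contrast and names no SSRT test. The Data Monitoring Plan (Data and Safety Monitoring) covers behavioural data only in general terms: "Data will be analyzed using the general linear model and regression analyses within SPM and SPSS".

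**The concern.** The scoring rule does not match the tracking rule. A staircase that settles at 50% inhibition finds the delay at which half of the go responses escape the stop process. That locates the median go RT, yet the plan subtracts the delay from the mean. Go RTs usually have a long right tail, so the mean exceeds the median and much of the gap is counted as stopping time.

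The project asks whether alcohol weakens inhibition, and each participant is scanned under both alcohol and saline. If alcohol made responding more variable, with more slow responses, the stated rule would report a longer SSRT even if stopping were unaffected. That false change could then be cited as behavioural support for a fall in BOLD activation.

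**Working it through.** **Plan's own figure.** There is none to reproduce. The documents give no SSRT value, RT distribution, power or effect size.

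**Inputs from the documents.** Three runs of 80 go and 40 stop trials give 3 × 80 = 240 go and 3 × 40 = 120 stop trials per session. The delay tracks 50% inhibition, and the score is mean go RT minus mean delay.

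**Assumptions not in the documents.** Independent race model; true SSRT 220 ms in every condition; ex-Gaussian go RT with Gaussian SD 50 ms and tail parameter tau; one-up/one-down staircase with steps of 20 to 50 ms.

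**Step 1: the algebra.** In the race model a response escapes when go RT < delay + SSRT. At 50% inhibition, P(go RT < delay + SSRT) = 0.5, so delay + SSRT ≈ median go RT. Hence

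stated score = mean − delay ≈ SSRT + (mean − median).

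**Step 2: size of the inflation.** Gaussian mean 400 ms, 50-ms step, trial SD of SSRT 30 ms; the simulated inhibition rate was 0.500 throughout.

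| tau (ms) | mean − median | stated score | excess over 220 | quantile score |
|---|---|---|---|---|
| 75 | 13.1 | 228.4 | 8.4 | 215.3 |
| 100 | 21.1 | 234.0 | 14.0 | 212.9 |
| 125 | 29.3 | 240.7 | 20.7 | 211.5 |
| 150 | 38.0 | 247.9 | 27.9 | 209.9 |

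The excess is 8.4/13.1 = 64% to 27.9/38.0 = 73% of the mean-median gap. It is less than the whole gap because the delay moves about during tracking. With a 20-ms step and no trial variation in SSRT, the excess at tau 100 is 18.7 of 21.1 ms.

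**Step 3: false alcohol effect, with stopping unchanged.** A second simulation used Gaussian mean 450 ms, a 50-ms step and saline tau 80.

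| alcohol tau (ms) | stated score | change from tau 80 | quantile score | change from tau 80 |
|---|---|---|---|---|
| 80 | 231.6 | 0 | 215.4 | 0 |
| 100 | 238.0 | +6.4 | 214.7 | −0.7 |
| 120 | 243.3 | +11.7 | 212.4 | −3.0 |
| 140 | 249.4 | +17.8 | 211.6 | −3.8 |

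The Step 2 table agrees. From tau 75 to 100, 125 and 150 the stated score changes by +5.6, +12.3 and +19.5 ms, and the quantile score by −2.4, −3.8 and −5.4 ms. Repeat runs of tau 80 to 120 at other settings gave about +10 to +15 ms for the stated score.

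**Step 4: what does not cause the error.** Moving the whole go distribution from a Gaussian mean of 400 to 440 ms at tau 75 left the stated score at 228.2 and 228.1 ms. The cause is skew, not slowing as such. Equal skew in both conditions gave a mean difference of about 0.

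**Step 5: what it could do to a test, if one were run.** In a paired alcohol-saline comparison with extra difference noise of SD 30 ms (assumed), two-sided 0.05 and tau 75 to 125, a significant false rise occurred in about 74% of trials at n = 60 and 42% at n = 30. With the quantile score the rate was at most 3% in every case.

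**Step 6: limits of the replacement.** The quantile score read 217.2, 213.1 and 210.2 ms at tau 50, 100 and 150, so it was about 3 to 10 ms low. Under upward RT drift of 100 and 200 ms over a session, both scores fell: the stated one from 228.2 to 222.2 and 215.6 ms, the quantile one from 215.1 to 208.9 and 203.3 ms. Dropping omitted go trials also harms the quantile score. At tau 80, 5% omissions took it from 215 to 207 ms and 10% to 198 ms. Assigning omissions the slowest RT brought the score with 5% omissions back to within about 1 to 2 ms of its no-omission value.

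**The case against.** The strongest reply is that no planned inference depends on SSRT. The aims, the primary outcome and every analysis in the Statistical Analysis Plan concern BOLD activation, and the BOLD contrast compares correct inhibition trials with correct go trials without using SSRT. This stands. A reader might infer that the primary results are biased, and the documents do not support that. A reader might also take the general sentence in the Data Monitoring Plan as committing the study to an SSRT test by drug, sex or phase. It names the modelling approach and the software, but no SSRT outcome or comparison.

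Second, the harm needs a premise that the documents do not supply, namely that alcohol changes the shape of the RT distribution. This also stands. It is tempting to extend the point to false sex or phase differences, but that would require the tail, or its change under alcohol, to differ by sex or phase. The documents do not say so and no simulation here examined it.

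Third, the quantile score has errors of its own. With tau rising from 80 to 120 ms and 5% omissions added under alcohol, the stated score moved about +2 ms, while a quantile score that ignored omissions moved about −12 ms, a false improvement. This limits the remedy: the quantile score needs an omission rule. It does not rescue the stated formula, whose small net error in that case comes from two errors offsetting.

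Finally, the task is attributed to a cited fMRI validation that cannot be seen here and may contain scoring detail. The rule written in this plan is nonetheless explicit, and nothing else in the documents modifies it.

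**Conclusion.** The point holds as a cheap improvement to a secondary measure. The stated formula overestimates SSRT when go RTs are right-skewed: by about 8 to 28 ms for tau of 75 to 150 ms under the Step 2 settings. Most of that is common to both conditions and cancels in the alcohol-saline difference if the skew is unchanged. What remains is a possible false rise of roughly 6 to 18 ms if alcohol lengthens the tail by 20 to 60 ms.

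That range rests on the assumed race model, ex-Gaussian RTs, staircase settings and tail change; none of these comes from the documents. The direction follows from the plan's own 50% rule together with right skew. No effect on the BOLD outcome, or on sex or phase comparisons, has been shown.

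**What to change.** In the Stop Signal Task description, replace the mean-based formula with the following:

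- For each session, preferably by run, compute SSRT as the quantile of the go RT distribution at the observed probability of responding on stop trials, minus the mean stop delay over the same trials.
- Keep omitted go trials in the distribution and assign them the slowest RT.
- Report go RT skew, omissions and slowing by condition, so that a reader can judge any SSRT difference.

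Scoring by run is meant to limit the effect of drift across the session; that benefit was not simulated.

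The cost is a modest scoring script, with no change to participant procedures. It needs trial-level responses. The plan does not say outright that these are stored, but sorting trials into correct inhibitions and correct go responses for the BOLD contrast already requires them. The remaining drawback is a score that reads a few ms low (about 3 to 10 ms in simulation), though it changes much less with tail length than the stated one.

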- *Research Repositories:* If the purpose of this submission is to establish a Research Repository (bank, registry) and the material you plan to collect is already available from a commercial supplier, clinical lab, or established IRB approved research repository, provide scientific justification for establishing an additional repository collecting duplicate material. Describe the repository design and operating procedures. For relevant information to include, see the [UK Research Biospecimen Bank Guidance](#) or the [UK Research Registry Guidance](#).

This study will use a within- and between-subjects, placebo-controlled, single-blind design in a sample of female (N=30) and male (N=30) young adult heavy drinkers. Subjects will attend four fMRI sessions (two in the early follicular phase and two in the mid-luteal

phase for women, and at matched intervals for men) in which they perform the stop signal task and a resting state undergoing either IV alcohol (60mg%) or saline infusion (placebo). Alcohol and saline sessions within each phase will be separated by 24-48 hours. Dose and phase order will be counter-balanced. Blood samples will be collected at baseline and during infusion to assess levels of estradiol, progesterone, and testosterone. The primary outcome measure will be brain activation during response inhibition.

Attachments

Subject Recruitment Methods & Advertising

Describe how the study team will identify and recruit subjects. Please consider the following items and provide additional information as needed so that the IRB can follow each step of the recruitment process.

- How will the study team identify potential participants?
- Who will first contact the potential subjects, and how?
- Will you use advertisements? If so, how will you distribute those?
- How and where will the research team meet with potential participants?
- If applicable, describe proposed outreach programs for recruiting women, minorities, or disparate populations.
- How will minimize undue influence in recruitment?
- Attach copies of all recruiting and advertising materials (emails, verbal scripts, flyers, posts, messages, etc.).

For additional information on recruiting and advertising:

- [IRB Application Instructions - Advertisements](#)
- [PI Guide to Identification and Recruitment of Human Subjects for Research](#)

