Determination of menstrual cycle phase. Women will complete a guided calendar-based interview to determine average menstrual cycle length and to estimate the onset of next menses (Roche and King 2015). Women will be randomly assigned to start in either the early follicular (2-7 days following the onset of menses) or the mid-luteal (5-10 days following ovulation) phase. Blood samples collected during each session will be used to retrospectively confirm that the targeted menstrual cycle phase was achieved. Ovulation will be confirmed by at-home urinary luteinizing hormone (LH) assays. Beginning on day 7 of their cycle, participants will complete the at-home LH assays every day, until a positive test is confirmed. They will be provided with small (2oz) cups and lids, as well as 20 LH tests. Each morning, they will use the cups to collect a small sample of urine. They will place the LH test (a short, paper stick) into the urine sample for 3 seconds, and then lie the test flat on the cup lid. Three minutes later, they will take a picture of the test and send it via text message to the Research Assistant. The RA will confirm whether the test is positive or negative. If negative, the RA will ask the participant to test again the next day, and if positive, the RA will inform the participant that she can stop the LH tests.

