4. Intravenous administration of alcohol: The possible adverse effects of alcohol include pain at the injection site, disorientation, or sedation. Nausea and/or vomiting are extremely unlikely given the moderate dose administered. No serious adverse effects have been reported in healthy men and women following intravenous administration of a 6% alcohol solution (Blekher et al. 2002; Davidson et al. 1997; Ray and Hutchinson 2004; Yoder et al. 2005). We have successfully administered a higher dose (80mg%) than that proposed here (60mg%) intravenously both in and out of the scanner (Weafer et al. 2018).

5. Pregnancy testing. There is a risk of psychological discomfort from exposure to a pregnancy test or the upset that might result from an unexpected non-negative outcome. These tests do, of course, require the participant's consent and cooperation, and all potential female participants are given advance notice of this test during initial phone contact. The PI's standard operation procedures will call for the exclusive use of a trained Research Assistant (RA) to give instructions, process the samples, and report the results to participants individually. The RA will advise participants of the conclusiveness of negative results and also stress the ambiguity of non-negative outcomes. The RA will explain that rather than repeating non-negative tests to try to rule out a possible false-positive, any

ambiguous result is grounds for disqualification. The assistant will also immediately offer specific advice about what precise follow-up testing and provide information about how to get counseling if desired.

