For additional considerations:

[Return of Research Results or Incidental Research Findings](#)

[HIPAA policies](#)

[FERPA policies](#)

[Procedures for Transfer agreements](#)

[Information regarding multi-site studies](#)

[NIH Genomic Data Sharing \(GDS\) Policy](#)

[Digital Data](#)

All research materials obtained from participants will be collected directly from them at the time of recruitment and participation. The research material consists of subjects' questionnaire scores, fMRI data (BOLD, CBF), hormonal assays (estradiol, progesterone, testosterone), behavioral performance on the stop signal task, and subjective reports (BAES, DEQ). No archival records or other data will be used. All data will be coded by participant numbers and any personal identifiers linking participants to their reports on questionnaires and computer tests will be maintained in a separate location by the PI. The data will then be transferred to computer files with all individual identifiers removed. All data will be stored in coded files and locked in the laboratory area. All information will be in the form of numerical data and used for research purposes only. Results will be reported only for groups, and no single individual will be identified. Personal identifiers, such as names, will be removed from the subjects' data records. Urine samples will be collected at screening, prior to a subject's participation in the experimental protocol. These urine samples will be tested for the presence of a full range of drugs of abuse. Drug urine screens and urine pregnancy tests will also be conducted daily during the experimental protocol. Expired air samples will also be taken at these times to detect the presence of recent alcohol consumption. Other research materials obtained from the volunteers include demographic information, mental and physical health screening information, experimental data, and non-intrusive staff observations. Experimental data include the stop signal task measures, fMRI BOLD/CBF data, hormonal assays, and self-reported responses on questionnaires.

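### Women are to be told that a negative pregnancy test is conclusive, although half of their sessions fall 5-10 days after ovulation, when a negative may not exclude conception in the current cycle

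*Combined protocol and SAP*

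**What the plan says.** The instruction is in Potential Risks & Benefits, item 5 (Pregnancy testing): "The RA will advise participants of the conclusiveness of negative results and also stress the ambiguity of non-negative outcomes". The sentences after it deal with non-negative results only. These disqualify without repeat testing and lead to advice on follow-up testing and counseling. Nothing there limits what a negative can show.

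The schedule is set elsewhere. Research Procedures (Determination of menstrual cycle phase) defines the two phases as "early follicular (2-7 days following the onset of menses") and "the mid-luteal (5-10 days following ovulation) phase", and adds: "Ovulation will be confirmed by at-home urinary luteinizing hormone (LH) assays". A research assistant reads those LH results, so the study knows roughly where in the cycle a luteal session falls. Study Design gives every woman two sessions in each phase, and states: "Alcohol and saline sessions within each phase will be separated by 24-48 hours". It also states: "Dose and phase order will be counter-balanced".

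Subject Recruitment Methods & Advertising identifies the pregnancy test as urine hCG. On timing, Data and Safety Monitoring says: "Women will provide a urine sample for a pregnancy test before each session". Records, Privacy, and Confidentiality says: "Drug urine screens and urine pregnancy tests will also be conducted daily during the experimental protocol". The Safety Monitoring Plan also excludes women who are planning a pregnancy. Phone screening asks about hormonal contraception, but no rule is attached to the answer and no contraception requirement is stated.

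**The concern.** The protocol treats false positives carefully and says nothing about false negatives, although the design deliberately tests women soon after ovulation. A test taken before hCG is detectable is negative whether or not conception has occurred in that cycle. Calling that result conclusive would then give more reassurance than the test supports, at the sessions that include one of each woman's two alcohol infusions.

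What is at stake is mainly the accuracy of what women are told. A woman told that her negative is conclusive has less reason to test again if her period is late, and less reason to tell the study.

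**Working it through.** The documents state no figure on this point, so there is none to reproduce. The check has two parts: how often the wording applies, and how much of the luteal window could precede detection.

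**Inputs from the documents.** 30 women; four sessions each, two per phase, one alcohol and one saline in each phase, 24-48 hours apart; luteal window days 5-10 after ovulation (six days); follicular window days 2-7 from menses onset; a urine test before each session; phase order counter-balanced.

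**Assumed inputs (not in the documents).** D, the first day after ovulation on which urine hCG is detectable: 5 to 14. L, luteal phase length: 12 to 16 days. p, conception probability per cycle: 0.1% to 2%, for illustration only.

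**Step 1: where the wording applies.** Female sessions: 30 × 4 = 120. Luteal sessions: 30 × 2 = 60. Luteal alcohol infusions: 30 × 1 = 30. Women whose luteal sessions come last: 30 / 2 = 15 under counter-balancing. The section on cycle phase speaks of random assignment to a starting phase; under simple randomisation the 95% range would be 10 to 20.

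**Step 2: share of the window before detection.** The number of window days earlier than D is min(D, 11) − 5, out of six. For a woman's two luteal tests together, there are nine possible day pairs in the window: five that are one day apart and four that are two days apart. Both tests precede detection when the later one does. The last column weights the nine pairs equally and multiplies by 15 luteal-last women.

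| D | Window days before D | Pairs with both tests before D | Of 15 luteal-last women |
|---|---|---|---|
| 5 | 0/6 | 0/9 | 0 |
| 6 | 1/6 (17%) | 0/9 | 0 |
| 7 | 2/6 (33%) | 1/9 | 1.7 |
| 8 | 3/6 (50%) | 3/9 | 5.0 |
| 9 | 4/6 (67%) | 5/9 | 8.3 |
| 10 | 5/6 (83%) | 7/9 | 11.7 |
| 11-14 | 6/6 (100%) | 9/9 | 15 |

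These counts describe test timing, not pregnancies.

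**Step 3: what luteal-first women get later.** Their follicular sessions fall on days L + 2 to L + 7 after the earlier ovulation: 14-19 for L = 12, 16-21 for L = 14, 18-23 for L = 16. All are at or beyond the top of the assumed range for D, and the sessions cannot be dated unless menses occurs. The schedule therefore supplies a later check for these women.

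**Step 4: expected events.** Conceptions in the luteal-session cycle are 30 × p: 0.03 at 0.1% and 0.6 at 2%. The chance of at least one, 1 − (1 − p)^30, is 3% to 45%. Among the 15 luteal-last women the expected number is 15 × p, or 0.015 to 0.3, with a chance of at least one of 1.5% to 26%.

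**The case against.** The strongest reply is that the deciding fact lies outside the documents. They give neither a test sensitivity nor a detection day, and if hCG is detectable by day 5 the point fails. That stands as a condition. But any later day leaves part of the window uninformative, and nothing in the documents supports an unqualified claim of conclusiveness either.

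Second, the protocol refers to standard operating procedures that are not supplied, and the consent pages were removed before review. A caveat may be in either. So it cannot be said that women receive no caveat, only that the written instruction contains none.

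Third, the item is about the discomfort of testing, and the sentence may only mean that a negative settles eligibility for that day's session. That is a fair reading of the intent. Even so, the sentence describes what participants are told, and they would hear a statement about whether they are pregnant.

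A reader might infer something stronger: that the absence of a stated menses or pregnancy check after the last session in luteal-last women is a design error, and that their debriefing should be held back to supply one. The documents do not support this. Nothing in them requires such a check, women planning pregnancy are excluded, and the debriefing already gives a contact at which questions can be asked. A delay of about two weeks for about 15 women, to catch an expected 0.015 to 0.3 conceptions, is hard to justify when advice at the session serves most of the purpose.

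Nor do the 60 sessions count uninformative tests. They are the sessions at which the wording is used; the share affected depends on D and may be zero.

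**Conclusion.** The point holds as a minor matter of participant information and safety. The instruction on negatives is unqualified, and half of the female sessions, including 30 alcohol infusions, fall in a window where it may be wrong. The conclusion rests on one assumption, that urine hCG is first detectable after day 5. On that assumption between one sixth and all of the window precedes detection.

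Several things keep it minor. Women planning pregnancy are excluded, luteal-first women are later dated from menses and retested, and few conceptions are expected (0.03 to 0.6 across 30 women at the illustrative rates). The infusion also adds little to the 10-30 drinks per week that these women must already report. The sample size, the comparisons and the imaging analysis are not affected.

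**What to change.** In the pregnancy-testing item and the research assistant's instructions, replace the claim of conclusiveness with a statement that a negative at a mid-luteal session does not rule out very early pregnancy in the current cycle. At those sessions, have the research assistant advise each woman to take a pregnancy test, and to tell the study, if her expected menses does not come. Report any exposed pregnancy through the adverse-event and unanticipated-problem route already set out under Data and Safety Monitoring. If the operating procedures or consent form already say this, bring the protocol sentence into line with them.

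The cost is one wording change and a sentence of advice at luteal sessions, which may cause slight added worry. No imaging session moves, no visit is added and the debriefing stays where it is.
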